
message conditions (0, 20, 40, 60, or 80 percent negativity), 2 conditions based on the placement of the negative portions (beginning or end), and 2 versions of each message condition to allow for the messages to be analyzed as random factors. A 5x2x2 design typically yields 20 cells; however, when there is 0% negative portions of a message, it is unnecessary to consider the placement of the negative portions that do not exist. This results in 18 conditions as opposed to 20 conditions.

Study Purpose/Objective

To understand how cancer patients react to and recall emotional support messages that contain different percentages of positive statements of empathy and caring and also negative statements of criticism and blame.

Study Aims

Aim #1: To determine how cancer patients rate emotional support messages that consist of differing percentages of negative statements (0, 20, 40, 60, or 80 percent) and messages in which those negative portions occur at either the beginning or end of the supportive message.

Aim #2: To determine what portions of emotional support messages that consist of differing percentages of negative and positive statements cancer patients recall in the minutes after reading a message, and whether the placement of the negative portions at either the beginning or end of the message also affects recall.

Hypotheses & Research Questions

Hypotheses 1-4 and Research Questions 1-4 address Study Aim #1.

H1: Cancer patients' ratings of message effectiveness differ based on the percentage of the support message that is negative.

RQ1: How, if at all, do cancer patients' ratings of message effectiveness differ depending on whether negative portions of messages occur at the beginning or end of the entire message?

H2: Cancer patients' ratings of supporter competence differ based on the percentage of the support message that is negative.

RQ2: How, if at all, do cancer patients' ratings of supporter competence differ depending on whether negative portions of messages occur at the beginning or end of the entire message?

H3: Cancer patients' likelihood of seeking support from a supporter in the future differs based on the percentage of the support message that is negative.

RQ3: How, if at all, do cancer patients' likelihood of seeking support from a supporter in the future differ depending on whether negative portions of messages occur at the beginning or end of the entire message?

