in the survey in the future. Participants also answer an open-ended question in which they are asked what specific phrases or sentences they recall from the support message they read.

During pilot tests of the questionnaire, the average time to complete was 7.5 minutes. Three weekly reminders will be sent by email to those who have not completed the survey to encourage participation. Those who opt out will not be contacted with follow-up emails. The recruitment emails will include a link that can be clicked to opt out of the recruitment process for the study.

See Appendix A for the questionnaire and Appendix B for the message conditions.

Planned Analyses

The number of participants was determined through power analyses performed by the statistical software program G*POWER. The suggested sample size provided by G*POWER was 479. Specifically, this was determined by conducting an *a priori* analysis with an effect size (f) of .25, alpha error probability of .05, power ($1 - \beta$ error probability) of .95, and 18 groups, which is the total number of message conditions listed above. Importantly, a power analysis using these same parameters but for an ANCOVA also yielded a suggested samples size of 479.

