Statistical analyses will consist of 5x2x2 nested factorial ANOVA models. The first study aim will be tested through 4 ANOVA models that will test for differences between participants who received the different messages in terms of 1) perceived message effectiveness, 2) perceptions of supporter competence, 3) likelihood to seek support from the supporter in the future, and 4) self-reports of emotional improvement. Depending on the correlations among the dependent variables, a MANOVA may be used instead of an ANOVA to test the first aim of the study. Similarly, if significant covariates (such as age or times since diagnosis) are found, the ANOVA/MANOVA could become an ANCOVA or MANCOVA. To test the second aim of the study, a chi-square analysis will test to see if participants recall negative portions of messages more frequently than positive portions of messages depending on which message they received (i.e., dependent on the position and percentage of the negative message portions). The second aim will also be tested using ANOVA models to determine if significant differences occurred in the number of negative words that were recalled across the 18 messages received (i.e., dependent on the position and percentage of the negative message portions). The software program LIWC (Linguistic Inquiry and Word Count) will be used determine the number of negative words recalled by the participants in their open-ended responses.

Potential Benefits

There are no benefits for being in this study; however, by joining this research study, the participant is helping to provide information which may help science and society.

Potential Risks

Because of the personal nature of the questions to be asked, the participant might reflect on unpleasant memories while completing the questionnaire. Although not expected to occur, it is

possible that a breach of confidentiality could occur if the computer on which the data file is stored is compromised or otherwise hacked or illegally accessed.

Compensation, Benefits, and Risks

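### The only planned comparison of negative with positive recall is a chi-square that either drops the amount recalled and ignores the amount available, or breaks independence

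*Combined protocol and SAP*

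**What the plan says.** Under Participation, each respondent reads one of 18 messages of 100 words and then answers an open question in which "they are asked what specific phrases or sentences they recall from the support message they read". The answer is a list, so it holds a graded measure for each person.

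Aim 2 (Study Aims) covers which portions are recalled and also "whether the placement of the negative portions at either the beginning or end of the message also affects recall". Under Hypotheses & Research Questions, H5 compares the frequency of negative and positive recall, H6 concerns the likelihood of negative recall as its percentage rises, and H7 concerns the number of negative words recalled.

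Planned Analyses gives two analyses for this aim. First, "a chi-square analysis will test to see if participants recall negative portions of messages more frequently than positive portions of messages", by position and percentage. Second, ANOVA models of the number of negative words recalled, counted with LIWC. The section does not say how an answer is coded for the chi-square, what the unit is, how the table is laid out, or what power it has. The sample size calculation in the same section is for an ANOVA with "effect size (f) of .25", "alpha error probability of .05" and 18 groups.

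**The concern.** A chi-square needs categories, and the plan can be read in three ways:

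- **One category per participant.** A person who recalls one critical phrase scores the same as a person who recalls all of them. The test also takes no account of how much criticism there was to recall.
- **Phrases as the unit.** The amount is kept, but several phrases come from one person and are not independent.
- **Both kinds tabulated for each person.** The negative and positive entries are paired, and an ordinary chi-square treats them as separate samples.

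The H7 ANOVA does not fill the gap. It has no positive count, so it cannot address H5. It also counts words that LIWC classes as negative, not phrases traced to the negative portion of the message.

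Two wrong conclusions are at stake. A significant result across percentages could be read as negativity bias when it reflects only how much negative text was shown. A null result for placement could be read as no effect when the yes/no score is near its ceiling and the amount recalled does differ.

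**Working it through.** **1. The plan's own figure.** For an 18-group ANOVA with f = .25, alpha = .05 and N = 479, the noncentrality is N·f² = 479 × .0625 = 29.94 on 17 and 461 df. Power is .950, and 479 is the smallest N that reaches .95. The figure reproduces, but it describes the ANOVA and not the chi-square.

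**2. Any-versus-none recall with no negativity bias.** Assume 10 statements per message, each recalled independently with the same probability q whether positive or negative. With k negative statements, P(any negative recalled) = 1 − (1 − q)^k.

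| Negative content | k | q = .25 | q = .35 |
|---|---|---|---|
| 20% | 2 | .44 | .58 |
| 40% | 4 | .68 | .82 |
| 60% | 6 | .82 | .92 |
| 80% | 8 | .90 | .97 |

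The rate about doubles from 20% to 80% at q = .25 with no bias at all. By symmetry, a 20% message (8 positive statements) gives .90 for any positive against .44 for any negative, and an 80% message gives the reverse.

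Now put the q = .25 rates into an 18 × 2 table with N = 479 (two messages at 0, four at each other level):

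- Mean rate: 4 × (.44 + .68 + .82 + .90)/18 = .631.
- Sum of squared deviations: 2 × .631² + 4 × (.191² + .049² + .189² + .269²) ≈ 1.384.
- Noncentrality: (479/18) × 1.384/(.631 × .369) ≈ 158.
- Power at 17 df is about 1.00. Without the 0% messages (16 groups, N = 426) it is still above .999.

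The test would therefore reject almost always under equal recall of every statement.

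**3. Phrases as the unit.** With equal allocation, the average negative content is (2×0 + 4×20 + 4×40 + 4×60 + 4×80)/18 = 800/18 = 44.4 words of 100. Within percentages it runs from 0 to 80. With no bias, the expected negative share of recalled phrases is therefore not one half overall or within most cells, and the plan states no null proportion. The non-independence is a separate problem.

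**4. Placement, by simulation.** All inputs are assumed: 10 statements; q = .15, .25 or .35; person SD 0.7 on the logit scale; placement log-odds shift 0.4. There are 8 cells (four percentages by two placements) of 53, so 424 people, close to 479 × 16/18 = 426. Two tests stratified by percentage are compared: an inverse-variance pooled difference in the share of negative statements recalled, and Mantel-Haenszel on any versus none.

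| q | Share recalled | Any versus none |
|---|---|---|
| .15 | .83 | .62 |
| .25 | .90 | .59 |
| .35 | .93 | .49 |

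A separate run of the same model gave .81, .88 and .93 against .61, .60 and .54, so these are approximate to about .05. False-positive rates were about 5% for both tests. As q rises, the share gains power and the yes/no score loses it, which is the ceiling shown in step 2.

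**The case against.** The strongest reply has four parts.

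- **Power.** A reader might infer that the chi-square falls well below the .95 for which the study was sized. The documents do not support that. The .95 and the 479 belong to the ANOVA, and no recall rate, effect size or table is given for the chi-square. At w = .25 and N = 479, chi-square power is .957 with 17 df and .9998 with 1 df. If a graded outcome with f = .25 is cut at its median (relative efficiency .64), 17-df power falls to .78 at 479, but it is .97 at the 800 named in Recruitment and Eligibility. The prize odds (5 × 120) suggest about 600, where it is .89. This reply stands.
- **The amount is analysed elsewhere.** The H7 ANOVA uses a count and covers position and percentage. This stands in part: negative words are graded, so a null chi-square on placement would not stand alone. Negative portions and positive recall still have no graded analysis.
- **The wording fits.** H5 speaks of frequency and H6 of likelihood. This stands for H6, where a yes/no outcome is the one named. For H5 it does not settle the unit, the pairing or the unequal amount of text.
- **The coding is inferred.** This is true, since the layout is not stated. But each of the three readings has a defect, so the gap does not rescue the sentence.

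The placement simulation compares two stratified 1-df tests, and neither is the plan's own test. It illustrates the information lost and does not estimate the study's power.

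**Conclusion.** The concern holds as a matter of validity and of unused information. The chi-square is the only planned comparison of negative with positive recall. Under each available reading it either drops the amount recalled and ignores the amount available, or treats dependent observations as independent. The effect of unequal availability follows from the design and is large: any-negative recall goes from .44 to .90 across percentages with identical recall of every statement at q = .25. The cost for placement depends on the assumed inputs: about .83, .90 and .93 for the share recalled against .62, .59 and .49 for any versus none. No shortfall against .95 is claimed.

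**What to change.** In Planned Analyses, replace the chi-square sentence with the following:

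1. Code each recalled phrase as coming from the negative or the positive portion of the message. For each participant, record the share of available negative statements recalled and the share of available positive statements recalled.
2. In the 16 mixed messages, with percentage and placement as factors, analyse the within-person difference (negative share minus positive share) for H5, and the negative share as well as the difference for placement. The gain shown above is for the negative share. The difference also carries the variation of the positive share, so it may be less sensitive to a placement effect on negative recall alone.
3. Leave the two 0% messages out of these analyses, because the negative share is undefined there.
4. Keep recall of any negative portion (yes/no) by percentage as the test of H6, and note that a rise is expected from availability alone.
5. Keep the LIWC ANOVA for H7.

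The cost is small. The answers must be classified for the chi-square in any case, so the extra work is a tally in place of a yes/no code and a count of statements in each message. The summary is slightly less simple to report. No new data or additional participants are needed.

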H4: Cancer patients' self-reports of emotional improvement after receiving a support message differs based on the percentage of the support message that is negative.

RQ4: How, if at all, do cancer patients' self-reports of emotional improvement after receiving a support message differ depending on whether negative portions of messages occur at the beginning or end of the entire message?

Hypotheses 5-7 address Study Aim #2.

H5: Cancer patients recall negative portions of supportive messages more frequently than they recall positive portions of supportive messages.

H6: As the percentage of negative portions of a supportive message increases, cancer patients likelihood to recall negative portions of supportive messages also increases.

H7: The number of negative words recalled from the supportive messages by cancer patients differ depending on the percentage of the message that is negative.

Methods

This is a cross-sectional, observational survey study. Data will be collected through a mass email disseminated through the online survey platform Qualtrics.

Recruitment and Eligibility

800 participants will be recruited from Moffitt TCC-consented patients who have agreed to be contacted for future research.

Inclusion Criteria: Living patients, 18 years of age or older, diagnosis of breast, prostate, thoracic, or digestive cancer in the past 3 years, consent to the Moffitt TCC protocol and indication of their willingness to be contacted for future research by including an email contact, and ability to read and write fluently in English.

A random selection of at least 800 patients who fit inclusion criteria will be drawn by Moffitt Collaborative Data Services. An invitation to participate in the current study will be sent to participants via an email disseminated through the online survey host Qualtrics. The contact list of email recipients will be uploaded into the Qualtrics system and the email will be sent from [name] (study team member). If a potential participant were to choose to reply to this email with questions about the study or for any other reason, these replies would be sent to [name], who would be tasked with responding to the potential participant's message. The invitation will include a description of the study and a link to the study survey.

Consent Process

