Because participation will occur solely online and consists only of an online questionnaire, the research team requests a waiver for written consent. Instead, we request that consent can be given by having participants read an informed consent statement on the opening page of the online questionnaire. Clicking to the next page and beginning survey would signify consenting to participate.

Participation

Participating in the study consists of taking an online questionnaire. The questionnaire begins with self-reported demographic questions (biological sex, age, ethnicity, time since initial cancer diagnosis, cancer site). Next, the participant is asked to think of someone they know well but who they did not directly disclose the news of their cancer diagnosis. Then, the participant is told to imagine receiving a written message of support from this person in the days after initially being diagnosed with cancer. The participant then reads one of 18 different emotional support messages randomly assigned through the Qualtrics survey system. These 18 messages are each 100 words long and systematically vary in how much of the message is composed of negative statements of criticism and positive statements of caring. The 18 message conditions are part of a 5x2x2 nested factorial design and are as follows:

- Two messages composed of only positive statements (0% negative).
- Two messages in which the last 20% of the message consists of negative statements of criticism.
- Two message in which the first 20% of the message consists of negative statements of criticism.
- Two messages in which the last 40% of the message consists of negative statements of criticism.
- Two message in which the first 40% of the message consists of negative statements of criticism.
- Two messages in which the last 60% of the message consists of negative statements of criticism.
- Two message in which the first 60% of the message consists of negative statements of criticism.
- Two messages in which the last 80% of the message consists of negative statements of criticism.
- Two message in which the first 80% of the message consists of negative statements of criticism.

The participants then answer a series of closed ended scales regarding quality of the support message, the supporter's competence, the amount of emotional improvement they experienced after reading the message, and the likelihood to seek support from the person they chose earlier

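### The recall chi-square compares negative with positive recall within the same participants, and it is miscalibrated unless each participant enters the table once, which the plan does not state

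*Combined protocol and SAP*

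**What the plan says.** - **Test.** For Aim 2, Planned Analyses names a chi-square to test whether "participants recall negative portions of messages more frequently than positive portions of messages depending on which message they received", glossed as "i.e., dependent on the position and percentage of the negative message portions". A separate ANOVA covers the number of negative words recalled.
- **Measure.** Under Participation, recall is collected by one open-ended question about "what specific phrases or sentences they recall from the support message they read".
- **Exposure.** Each person sees a single message: "The participant then reads one of 18 different emotional support messages randomly assigned through the Qualtrics survey system". Two of the 18 messages are wholly positive. The other 16 mix positive and negative text.
- **Questions.** "H5: Cancer patients recall negative portions of supportive messages more frequently than they recall positive portions of supportive messages". H6 concerns negative recall alone, rising with the negative percentage. Aim 2 also asks "whether the placement of the negative portions at either the beginning or end of the message also affects recall".

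The plan does not say whether the chi-square counts participants, kinds of recall or phrases, or whether the categories are mutually exclusive. It names no paired or clustered method.

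**The concern.** A Pearson chi-square assumes that every count comes from a separate, independent unit. Message, percentage and placement vary between participants, so randomisation takes care of that margin. Valence (negative or positive) does not: a reader of a mixed message can recall both kinds, or several phrases of one kind. A table with valence as a margin can therefore hold the same person more than once.

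The direction of the error depends on how the table is filled, and the plan leaves that open. One plausible layout would miss real differences and another would produce false ones. H5 is the clearest case, because it directly contrasts two outcomes measured on the same people. The chi-square is also the only planned test of how often each kind is recalled, since the ANOVA counts negative words only.

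**Working it through.** **1. The plan's own figure.** With one-way ANOVA, f = .25, alpha .05 and 18 groups, the noncentrality is .25² × 479 = 29.94 on 17 and 461 df. Power is .9502, so 479 reproduces. It was derived for the ANOVA; no sample size is given for the chi-square. The mixed messages would hold 479 × 16/18 ≈ 426 participants.

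**2. Assumptions.** The documents give no recall rates, phrase counts or within-person correlations. Those below are assumed. All false-positive rates are at nominal .05 with no true difference.

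**3. Phrases pooled.** With m phrases per person, the statistic is inflated by about 1 + (m − 1) × ICC. The false-positive rate is P(χ² > critical value ÷ inflation), with critical values 3.841 (placement, 1 df) and 24.996 (16 messages, 15 df).

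| m | ICC | Inflation | Placement | 16 messages |
|---|---|---|---|---|
| 2 or 3 | 0 | 1.0 | 5% | 5% |
| 2 | .1 | 1.1 | 6.2% | 9.0% |
| 2 | .5 | 1.5 | 11% | 34% |
| 3 | .3 | 1.6 | 12% | 41% |
| 3 | .5 | 2.0 | 17% | 64% |

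Simulations agree: 6–17% for placement and about 10–65% over 16 messages for ICC .1–.5. With 5 phrases and ICC .3, simulation gives 18% and 74%.

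**4. Each person counted once per kind recalled.** Let 60% recall each kind, with correlation r between the two yes/no outcomes, and n people per placement.

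- Variance that the chi-square assumes for log(negative count ÷ positive count): (1/.6 + 1/.6)/n = 3.33/n.
- True variance: [2 × .4/.6 − 2r × .24/.36]/n = 1.33(1 − r)/n.
- Ratio: .4(1 − r).

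For r = −.3, 0 and .3 the ratio is .52, .40 and .28. P(χ² > 3.841 ÷ ratio) is then .0066, .0019 and .0002. Simulation gives .006, .002 and under .001. With 60% and 50% recall and latent correlation down to −.6, the simulated maximum for a two-group split is .014.

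The cost is power. If negative recall is truly 53% in one placement and 67% in the other, this table has power of about .12–.20. A participant-level test of the same negative-minus-positive difference has about .46–.71, with about 5% false positives.

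The formulas in steps 3 and 4 give false-positive rates that do not depend on sample size, so recruiting nearer 800 would not cure the miscalibration.

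**5. One entry per participant.** With negative recall yes/no by message, simulated rates are .047 (16 messages), .053 (2 groups) and .050 (4 groups). Classifying each person as recalling more negative than positive, or not, gives .046–.052. Both are valid.

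**6. H5 by an unpaired 2×2 chi-square.** With 50% recall of both kinds, true ÷ assumed variance is 1 − φ, where φ = (2/π) arcsin ρ and ρ is the latent correlation. At ρ = −.6, φ = −.41 and P(χ² > 3.841/1.41) = .099 (simulated .103). At ρ = +.6, φ = .41 and P(χ² > 3.841/.59) = .011 (simulated .012). At ρ = 0 it is .05. McNemar's test stays at .048–.056 throughout.

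**7. Which model term answers H6.** Hold negative recall flat at 60%, so that H6 is false, and let positive recall fall as positive text shrinks. A trend test on the negative-minus-positive difference rejects in about 58–62% of runs when positive recall falls from 70% to 50%, and in about 91–92% when it falls from 75% to 45%. A test of negative recall alone stays at about 5%.

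**The case against.** The strongest reply is that the subject of the planned test is the participant. Each participant reads one randomly assigned message, so classifying each person once and tabulating by message gives independent rows. Step 5 shows that this table is valid, and the plan does not exclude it. This stands. A reader might infer that the planned p-values for percentage and placement are simply wrong. The documents do not support that, because both are between-participant factors and the error appears only if a person can enter the table more than once.

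A reader might also infer that placement has no usable test of its own. That too goes beyond the text. Planned Analyses names both position and percentage without fixing the chi-square's layout. The ANOVA on negative words uses one value per participant, also addresses both factors, and is untouched by this problem.

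It is also fair that the sizes rest on assumptions, that the highest rates need the larger correlations and the 16-message table, and that ICC 0 gives no inflation.

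The reply does not dispose of the point. The valid coding is not stated. A yes/no table of negative recall does not compare negative with positive recall. H5 is paired under any coding that keeps both outcomes.

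**Conclusion.** The concern holds in a conditional form. The named test does not suit the negative-versus-positive contrast that the plan describes, and it is miscalibrated unless each participant enters the table once. If people count once per kind recalled, the placement false-positive rate is about 0.6% or less (60% recall of each kind, correlation −.3 to .3). If phrases are pooled, it is about 6–17% for placement and 10–65% over 16 messages (2–3 phrases, ICC .1–.5), falling to 5% at ICC 0. For H5, an unpaired chi-square ranges from about 1% to 10%, depending on the correlation. All recall rates, phrase counts and correlations are assumed. The ANOVA on negative words and the figure of 479 are not in question here. This should be settled before the recall data are analysed.

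**What to change.** Make the participant the unit and code two yes/no outcomes: any negative portion recalled, and any positive portion recalled. Use the 16 mixed messages, since negative recall is impossible for the two all-positive ones.

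1. **H5:** McNemar's test, or the valence term of a logistic GEE clustered on participant.
2. **H6:** a logistic model of negative recall alone, one row per participant, with percentage and placement as separate terms and message version included (the introduction intends messages to be analysed as random factors).
3. **Whether the negative-versus-positive difference varies by percentage or placement:** the valence × percentage and valence × placement terms of the clustered GEE. Do not use these terms as the test of H6, because they also respond to falling positive recall (step 7).

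Do not run a Pearson chi-square on pooled phrases or overlapping columns.

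The cost is a few sentences in Planned Analyses and a little more analysis, with no extra data or participants. P-values may be less favourable than from pooled phrases.

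### The chi-square by message received pools placement with percentage and message version, so it cannot answer Aim 2's placement question for recall frequency

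*Combined protocol and SAP*

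**What the plan says.** Study Aims, Aim #2, has two parts: what is recalled at each percentage of negative content, and "whether the placement of the negative portions at either the beginning or end of the message also affects recall".

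Under Hypotheses & Research Questions, each Aim 1 hypothesis (H1-H4) is paired with a placement question (RQ1-RQ4). For recall the text says only "Hypotheses 5-7 address Study Aim #2". None of those three hypotheses mentions placement, and there is no recall research question. H6 expects a percentage effect: "As the percentage of negative portions of a supportive message increases, cancer patients likelihood to recall negative portions of supportive messages also increases".

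Under Planned Analyses, recall frequency has one test, a chi-square that sets recall of the negative parts against "positive portions of messages depending on which message they received (i.e., dependent on the position and percentage of the negative message portions". Neither the table layout, nor the unit of count, nor any stratification is given.

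The same section adds a second recall analysis: "The second aim will also be tested using ANOVA models to determine if significant differences occurred in the number of negative words that were recalled". It opens with "Statistical analyses will consist of 5x2x2 nested factorial ANOVA models", and the design paragraph before Study Purpose/Objective makes placement one of the factors. That paragraph also provides two versions of each condition so that messages can be treated as random.

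**The concern.** A contingency chi-square over messages has no placement term. Differences due to percentage, placement and version all feed the same statistic. Two features of the design push it towards significance without any placement effect: the two 0% messages contain nothing negative to recall, and H6 anticipates a gradient across percentages. A significant result would say that recall differs somewhere among the messages, but not that placement matters, in which direction or by how much. When placement is the only effect present, spreading it over many degrees of freedom costs power. The second half of Aim 2 would then go unanswered for recall frequency.

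**Working it through.** **The plan's own figure.** Inputs from Planned Analyses: f = 0.25, alpha 0.05, power 0.95, 18 groups. For the noncentral F test, df1 = 17, df2 = N - 18 and lambda = f² × N = 0.0625 × 479 = 29.9. Power is 0.9502 at N = 479 and 0.9496 at N = 478, so 479 is reproduced. That calculation is for the ANOVA. The documents give no power and no recall rates for the chi-square, so every rate below is an assumption.

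**Why the 0% messages dominate.** Take equal allocation, no placement effect, and a flat 0.30 chance of recalling a negative portion in the 16 mixed messages.
- Pooled rate: (16/18) × 0.30 = 0.267.
- Participants in the two 0% messages: 2 × 479/18 = 53.2, with no recalls by construction.
- Each message contributes (x - n·p)²/(n·p·(1 - p)). With x = 0 this is n·p/(1 - p), so the two together give 53.2 × 0.267/0.733 = 19.4.
- The 5% critical value on 17 df is 27.6. Sampling variation in the other 16 messages usually supplies the rest.

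**Simulation.** N = 479, equal allocation, 3,000 runs per row, outcome negative portion recalled (yes/no), zero recall in the 0% messages, no message-to-message variance. Entries are the share of runs with p < 0.05. The last column is a Cochran-Mantel-Haenszel (CMH) test of placement stratified by percentage.

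| Assumed recall, 20% to 80% negative | Placement effect | 18 messages | 16 mixed messages | CMH, placement |
|---|---|---|---|---|
| flat 0.15 | none | 34% | 4% | 4% |
| flat 0.30 | none | 97.5% | 5% | 5% |
| flat 0.50 | none | 100% | 5% | 5% |
| 0.40 rising to 0.60 | none | 100% | 41% | 6% |
| 0.35 rising to 0.65 | none | 100% | 86% | 5% |
| 0.20 rising to 0.80 | none | 100% | 100% | 5% |
| flat 0.50 | 15 points | 100% | 45% | 88% |
| 0.35 rising to 0.65 | 15 points | 100% | 98% | 89% |

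If all 18 messages had the same recall rate, the 18-message test would reject 5.6% of the time. At N = 800 the flat 0.15 row rises from 34% to 75%.

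**Allowing messages to differ.** The 16 mixed messages form 8 percentage-by-placement cells of two, so placement tested against message variation has 16 - 8 = 8 error df. The assumed recall was 40/55/70/80% or 50/60/70/80%, and the placement log-odds ratio was 0.65 (odds ratio e^0.65 = 1.9). Power at N = 479:
- message SD 0: about 72-78%
- message SD 0.3 logits: 56-58%
- message SD 0.5 logits: 37-41%

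A model that ignores message variation gives 86-87% under the same effect, but only if that variation is truly zero.

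**Fixed message effects do not work.** Each message sits in one cell, so a model with fixed message effects has rank 16 with or without a placement column. Placement is fully aliased.

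**The case against.** Four points can be made for the plan.

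- **Aim 2 does have a placement test.** A reader might infer that placement goes untested for recall altogether. The documents do not support that: the factorial ANOVA on negative words recalled can carry a separate placement term. This stands. But a word count is a different outcome from whether a portion was recalled, and it does not cover recall of positive portions, which H5 compares.
- **The layout is not stated.** Naming both position and percentage could mean separate tables. Placement is randomised and crossed with percentage in the 16 mixed messages, so a simple placement-by-recall chi-square would be unconfounded and would hold its 5% level if messages did not vary. It is therefore too strong to say that no chi-square could answer the question. The point concerns the test by message received, which is what the text describes.
- **A positive result is not certain.** It depends on assumed recall rates. With the 0% messages dropped, flat recall and no message variation, rejection is about 5%. The simulated yes/no outcome is also only one reading of a comparison that the plan leaves undefined. This stands as a limit on the size.
- **Misreporting is not in the plan.** A reader might infer that the investigators will report a significant chi-square as a placement effect. The documents do not say so.

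**Conclusion.** The point holds for recall frequency. Placement is an explicit part of Aim 2, no Aim 2 hypothesis names it, and the one recall-frequency test described does not isolate it. A significant result by message cannot support a placement conclusion. With no placement effect, the 18-message test is significant in 97.5-100% of runs at N = 479 when assumed recall in the mixed messages is 0.30 or more, flat or rising as simulated, and in all runs of the three rising scenarios. It is significant less often when recall is rare. When placement is the only effect, the 16-message test has 45% power, against 88% for a stratified placement test, assuming no message variance. The sample size of 479 is not called into question, since it was set for the ANOVA. This should be corrected, but it is not a failure of Aim 2 as a whole.

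**What to change.** 1. Add an Aim 2 research question on placement and recall, in parallel with RQ1-RQ4.
2. Define the recall-frequency outcome: per participant, a negative portion recalled (yes/no) and, separately, a positive portion recalled (yes/no).
3. Replace the chi-square by message with a logistic model on the 16 mixed messages: percentage (20/40/60/80), placement (beginning/end) and their interaction. Enter message version as a random effect nested in the percentage-by-placement cell, as the design paragraph intends, and not as a fixed effect.
4. Report the placement odds ratio averaged over percentage with its 95% CI. State the averaging, because with an interaction in the model there is otherwise no single placement odds ratio. Fit the same model for positive portions.
5. Keep the ANOVA on negative words, and state that its placement term addresses Aim 2 for that outcome.

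The cost is plan wording and one standard model on data already to be collected, with no extra participants or items. The downside is precision: with two messages per cell, power for placement falls as messages vary (the 72-78%, 56-58% and 37-41% figures above). The 86-87% figure should not be quoted as the expected power.
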